6.1.4 Days 0-7 Post-Vaccination

During each study vaccination visit the study team will provide the subject with a diary that they will use to document unsolicited and solicited adverse reactions. This would include local symptoms (e.g. injection site pain, erythema, and swelling) and systemic symptoms (e.g. fatigue, headache, myalgia, nausea, and fever). In addition, each subject will be provided a thermometer and instructions for how to use in order to monitor fever post-vaccination.

On Day 3 post-vaccination the study team will perform a reminder phone call to each study participant to ensure subjects are compliant with safety event reporting on the diary (aka Diary compliance phone call on the Schedule of Events). The study team will also review and complete the safety follow up questionnaires with the subject.

On Day 7 post-vaccination the study team will perform a structured phone call with each study participant to review the information recorded by the subject in the diary (aka Safety follow-up phone call on the Schedule of Events). The study team will review and complete the safety follow up questionnaires with the subject. A study investigator will be notified if the subject reports symptoms that require further medical review, which could result in an Unscheduled Visit being conducted.

Patient will be provided a dairy to record symptoms from post-vaccination through day 7. If any solicited signs and symptoms reported in the diary are not resolved by the Day 7 contact, the subject will continue to record their daily symptoms in the diary until the Day 28 Visit or until they are resolved, whichever comes first.

Events will be followed until resolution or until clinically stable.

6.1.5 Days 14 (+/- 7 Day) and 28 (+/- 7 Days)

Anti-SARS-CoV-2 spike protein antibody and anti-SARS-CoV2 nucleocapsid total antibody levels will be obtained during these study event periods. Study team will record any changes to concomitant and immunosuppressant medications or therapies, as well as changes to health status to determine any potential adverse events. Blood will be collected for a platelet count and for mechanistic studies (Day 28 only). After Day 28, subjects randomized to a change in their immunosuppression medication will revert back to their original regimen. COVID-19 symptoms will be assessed to determine if the subject has experienced any COVID-19 symptoms or recently been tested. Patient and graft status information will also be collected. The study team will review and complete the safety follow up questionnaires with the subject.

If necessary, a symptom directed physical exam can be performed.

Segment II (described in Section 6.2) will begin on Day 28 for individuals whose immunosuppression regimen was not changed and continue to have low to no response levels for their COVID-19 spike protein test.

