1.5.2.1 Thrombosis with Thrombocytopenia Syndrome [TTS]

Thrombosis in combination with thrombocytopenia (thrombosis with thrombocytopenia syndrome [TTS]), in some cases accompanied by bleeding, has been observed very rarely following vaccination with the Janssen Ad26.COV2.S vaccine. Reports include severe cases of venous thrombosis at unusual sites such as cerebral venous sinus thrombosis (CVST), splanchnic vein thrombosis, and arterial thrombosis, in combination with thrombocytopenia. Cases of TTS occurred mostly within the first 3 weeks following vaccination, in males and females 18 years of age and older and were reported more frequently in females under 50 years of age. Fatal outcomes have been reported. The exact physiology of TTS is unclear. Thrombosis with thrombocytopenia, following administration of Ad26.COV2.S has a clinical course that resembles autoimmune heparin-induced thrombocytopenia (HIT) (Areppally

2021). Individuals who have experienced TTS or HIT are not eligible for participation in clinical studies.

Individuals diagnosed with thrombocytopenia within 3 weeks after vaccination should be actively investigated for signs of thrombosis. Similarly, individuals who present with thrombosis within 3 weeks of vaccination should be evaluated for thrombocytopenia.

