1.5.2.3 Immune Thrombocytopenia

No cases of immune thrombocytopenia have been reported in the context of clinical studies. Very low platelet levels (<20,000 per μ L) have been reported very rarely in the post-marketing setting typically within the first four weeks after receiving the Janssen Ad26.COV2.S vaccine. Some of these cases occurred in individuals with a history of immune thrombocytopenia (ITP).

Healthcare professionals should assess an individual's relevant medical history prior to administering the Janssen Ad26.COV2.S vaccine. If an individual has a history of ITP, discuss the risks and benefits of developing low platelet levels before administering the vaccine.

Healthcare professionals should be alert to signs and symptoms of ITP, such as spontaneous bleeding, bruising or petechiae. It is recommended to monitor platelet levels in individuals with a history of ITP following vaccination with the Janssen Ad26.COV2.S vaccine. If ITP diagnosis is confirmed, promptly initiate appropriate medical intervention.

Vaccine-associated Enhanced Disease, Including Vaccine-associated Enhanced Respiratory Disease

VAED, refers to an AE characterized by an exacerbated course of a vaccine-preventable disease following vaccination. The phenomenon has been observed primarily in vaccines targeting respiratory viruses, including RSV and SARS-CoV1, leading to it being commonly referred to as VAERD.

VAED/VAERD has been linked to a non-protective antibody response of low affinity for the target vaccine antigen. Subsequent natural infection leads to immune complex formation and complement activation with a Th2 biased CD4 T-cell response. In the case of VAERD, this results in pulmonary injury due to eosinophilic pulmonary infiltrations ([Munoz 2021](#)).

No cases of VAED/VAERD have been reported following vaccination with Ad26.COV2.S both in the clinical trial and post-marketing setting.

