5.2 Treatment Regimen

5.2.1 Immunosuppression Adjustment

Immunosuppression adjustment will occur 2 weeks prior to receiving the Janssen Ad26.COV2.S vaccine and continue for 28 days receiving the Janssen Ad26.COV2.S vaccine.

Given that transplant patients are maintained on immunosuppressive regimens that vary slightly, immunosuppression adjustment will need to be somewhat individualized to the patient. However, general rules can be implemented.

Two weeks prior to receiving the Janssen Ad26.COV2.S vaccine, patients randomized to immunosuppression adjustment (or offered immunosuppression adjustment in Segment II) will be considered individually and adjustments will be made by a nephrologist with knowledge of the patient's clinical situation. General rules for adjustment are as follows:

1. For patients receiving mycophenolate mofetil (MMF) or azathioprine (AZA), a calcineurin inhibitor (CNI) (typically tacrolimus or cyclosporine), and Prednisone. Adjustment will involve stopping MMF or AZA and starting 10 mg Prednisone/day. **Note:** most patients will be in this group.
2. For patients not on MMF, but on CNI and Prednisone, the CNI dose will be decreased by 50%,
3. For patients on belatacept, which is typically taken with MMF and Prednisone, MMF will be stopped, and belatacept and Prednisone will be modified to 10 mg a day.
4. Other patients are adjusted on a case-by-case basis by the sponsor-investigator and the co-investigators—ex. Tac-mTOR inhibitor—Reduce Tac by 50%.

28 days after receiving the Janssen Ad26.COV2.S vaccine, study subjects in this arm will resume their prior doses of immunosuppression and will be followed as per protocol and as clinically indicated by the transplant team.

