6.4 Unscheduled Visit

This visit will occur in Segments 1 and 2 if there are any medical event which would require follow up with a physician. This would be a clinical visit and contain a nephrology consult (if needed), a symptom directed physical exam, vital signs, and collection of the patient and graft status. This may include additional care if the sponsor-investigator believes it to be necessary for the health of the participant (COVID-19 surveillance, review of medications, etc.).

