6.6 Schedules of Events

Schedule of Events 1: Initial Responders, No Vaccination with Janssen Ad26.COV2.S Vaccine (COVID Spike Protein results ≥ 250 U/mL)

Study Event	Day -21	Day 0 ^a	1 Year	2 Years
Visit Description	Screening/ Consent			
Visit Window	-30/+7 Days		+/- 60 Days	+/- 60 Days
Informed Consent	X			
Demographics, Medical History	X			
Immunosuppressive Medication Data	X		X	X
Concomitant Medications and Therapies	X			
Anti-SARS-CoV-2 spike protein antibody test ^b	X ^b			
Anti-SARS-CoV-2 Nucleocapsid Total Antibody Test	X ^b			
COVID-19 Surveillance and Evaluation	X		X	X
Patient and Graft Status	X		X	X
Mechanistic Immunologic Studies ^c		X		

a For this cohort, Day 0 is generally defined as the point at which they are deemed to have anti-spike protein antibody levels ≥ 250 U/ml and thus not part of Segment I. Given that the windows of the 1 and 2 year assessments are wide, the follow up in this group will not differ from the follow-up in the other cohorts.

b Anti-SARS-CoV-2 spike protein antibody and Anti-SARS-CoV-2 Nucleocapsid Antibody tests will occur after consent has been obtained. The results of the anti-SARS-CoV-2 spike protein antibody levels will determine in which group the subject will participate.

c Defined in Section 3.1.4

**Schedule of Events 2A: Segment I, Low Responders
(No Change in Immunosuppression Medication)**

Study Event	Day - 21	Baseline Day 0	Day 3	Day 7	Day 14	Day 28	Day 90	Day 180	1 Year	2 Years	Unscheduled Visit ^a		
Visit Description	Screening	Janssen Ad26.COv2.s vaccine			Follow Up								Safety
Visit Window	-30 / +7 Days	-4/+1 day	+/- 1 Day	+/- 2 Day	+/- 7 Day	+/- 7 Days	+/- 15 Days	+/- 30 Days	+/- 60 Days	+/- 60 Days	N/A		
Informed Consent	X												
Demographics, Medical History	X	X											
Concomitant Medications and Therapies	X	X			X	X					X		
Immunosuppression Medications	X	X							X	X	X		
Nephrology Consult		X									X (as needed)		
Complete Physical Exam		X											
CBC with Diff (Platelet Count) ^b		X				X							
Tacrolimus, cyclosporine and/or MMF Drug Levels ^o		X											
Vital Signs ^c		X									X		
HcG Pregnancy Test ^d		X											
Janssen Ad26.CoV2.S Dosing		X											
Risk Factor Assessment and Kidney Transplant Follow Up Questionnaire		X							X				
Anti-SARS-CoV-2 spike protein antibody test	X ^e	X ^f			X	X	X	X	X ^r				
Anti-SARS-CoV-2 Nucleocapsid Total Antibody	X ^e	X ^f			X	X	X	X	X ^r				
Mechanistic Immunologic Studies ^g		X				X				X ^h			

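### As tabulated in Schedules 2A, 2C and 3, the only scheduled post-dose platelet count falls on Days 21-35, mostly after the three-week TTS period; Section 6.1.5 is unclear on whether a Day 14 count is also due

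*Combined protocol and SAP*

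**What the plan says.** **Visit text.** Section 6.1.5 covers Day 14 (+/-7 days) and Day 28 (+/-7 days) in one paragraph. Its only sentence on platelets is: "Blood will be collected for a platelet count and for mechanistic studies (Day 28 only".

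**Schedules (Section 6.6).** The row "CBC with Diff (Platelet Count" is marked as follows:

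| Schedule | Group (planned doses) | Pre-dose | Post-dose |
|---|---|---|---|
| 2A | Low responders (100) | Day 0 | Day 28 |
| 2C | Non-responders, immunosuppression changed (150) | Day 0 | Day 28 |
| 3 | Segment II (0 to 250) | Day 56 | Day 84, which is 28 days after the second dose |
| 2B | Non-responders, immunosuppression unchanged (150) | Day 0 | Reads as Day 14, but see the working |

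**Risk period.** Section 1.5.2.1 states: "Cases of TTS occurred mostly within the first 3 weeks following vaccination". It adds: "Individuals diagnosed with thrombocytopenia within 3 weeks after vaccination should be actively investigated for signs of thrombosis". It also gives the reverse rule, that thrombosis presenting in the same period calls for a platelet evaluation. For very low platelet levels, Section 1.5.2.3 gives a longer period: "typically within the first four weeks after receiving the Janssen Ad26.COV2.S vaccine".

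**Reporting.** Sections 1.5.2.1 and 7.2.2.1 list three criteria for a suspected AESI. Two are platelet criteria: a count below 150,000/µl without an identifiable alternative cause, and a count below 150,000/µl with a fall of at least 25% from baseline.

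**The concern.** The plan names a three-week period for TTS, attaches an action to thrombocytopenia found in that period, and makes a platelet fall reportable on its own. In Schedules 2A, 2C and 3, however, no scheduled count falls before Day 21. The earlier checks there rest on symptoms: the safety questionnaires with the Day 3 call, the Day 7 contact ("On Day 7 post-vaccination the study team will perform a structured phone call") and the Day 14 visit. An unscheduled visit is described as one that would "contain a nephrology consult (if needed), a symptom directed physical exam, vital signs, and collection of the patient and graft status", so a platelet count is not among its listed content.

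At stake is how complete the suspected-AESI data are for platelet falls without symptoms. Counts done in routine care may find some of these, but the documents give no frequency for them. Sites also cannot tell from Section 6.1.5 whether to count platelets at Day 14.

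**Working it through.** The plan gives no figure to reproduce here. The check is a reading of the table columns and a count of days.

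**1. Are the three marks reliable?** Rows whose timing the text fixes serve as a control. Section 6.1.4 puts the diary call on Day 3 and the safety call on Day 7. Both print in the right columns in 2A and 2C, and at 3 and 7 days after the second dose in Schedule 3. Schedule 3 does have displaced rows. The return to prior immunosuppression prints under Day 146, although Section 5.2.1 says that 28 days after the dose "study subjects in this arm will resume their prior doses of immunosuppression", which is Day 84. The physical exam also prints under Day 59, after the Day 56 dose that it should precede. The platelet mark at Day 84 nevertheless agrees with 2A and 2C.

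**2. Is the 2B mark reliable?** By the same control, no. The diary call and the safety call both print under Day 0 instead of Days 3 and 7, and the symptom-directed exam starts under Day 7, whereas 2A starts it at Day 14. Some 2B rows do align (spike antibody, mechanistic studies), but the platelet mark cannot be trusted. The likely explanation is a Day 28 mark moved one column to the left when the table was turned into text.

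**3. Window against risk period.**
- Day 28 +/-7 = Days 21 to 35, which is 15 days. Day 21 is the only one within three weeks, so 15 - 1 = 14 fall after it.
- Schedule 3: 84 - 56 = 28 days after the dose, so the result is the same.
- Day 14 +/-7 = Days 7 to 21: 15 of 15 days within three weeks.
- Against the four weeks of Section 1.5.2.3, Days 21 to 28 of the Day 28 window qualify: 8 of 15.

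**4. Doses affected, if the schedules are followed.**
- 2A + 2C: 100 + 150 = 250 of 400 Segment I doses (62.5%).
- If 2B is also Day 28: 250 + 150 = 400 of 400.
- Every Segment II dose (0 to 250) is added.
- If visits spread evenly over the window (assumed), 250 x 1/15 = about 17 doses get a count within three weeks and about 233 do not. For 400 doses, 400 x 14/15 = about 373 do not.

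**5. Illustration of detection.** Assume that a symptom-free fall starts on day o, spread evenly over Days 1 to 21, and is present from day o to day o + L - 1. Assume that the visit day v is spread evenly over its 15-day window. For one visit, the chance of detection is the number of (o, v) pairs with o <= v <= o + L - 1, divided by 21 x 15 = 315. For both visits, taken as independent, average 1 - (1 - p14)(1 - p28) over o, where p14 and p28 are the chances at each visit for that onset day.

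| Duration L (assumed) | Day 28 only | Day 14 only | Both |
|---|---|---|---|
| 7 days | 28/315 = 9% | 105/315 = 33% | 40% |
| 14 days | 105/315 = 33% | 182/315 = 58% | 79% |
| 21 days | 210/315 = 67% | 210/315 = 67% | 98% |

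The documents give no duration, onset pattern or visit distribution, so these percentages are illustrative only.

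**6. The two readings of Section 6.1.5.** If the qualifier covers both items, the text agrees with 2A, 2C and 3, and the late timing is what the plan intends. If it covers the mechanistic studies alone, counts are due at Day 14 and Day 28, and those three schedules contradict the text.

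**The case against.** **The text may already require the Day 14 count.** The qualifier stands next to the mechanistic studies, and the sampling table in Section 3.1.4 has mechanistic samples at Day 28 and none at Day 14. At a site that reads the sentence this way and follows it, there is no gap. This stands as a fair reading. It does not dispose of the point, because a site working from the schedule would still take a single count at Day 28.

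**TTS itself is covered by other routes.** TTS requires thrombosis together with thrombocytopenia, and thrombosis would usually be expected to cause symptoms. The questionnaires and calls ask about these, the reverse rule in Section 1.5.2.1 sends a patient with thrombosis for a platelet evaluation, Section 6.4 allows additional care beyond its list, and Section 7.2.2.1 asks for anti-PF4 testing for either component. The instruction to look for thrombosis depends on a diagnosis of thrombocytopenia; it does not require screening. All of this stands, and it narrows the gap to symptom-free platelet falls.

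**The illustration depends on its assumptions.** This also stands. At an assumed 21 days, a single count at Day 28 does as well as one at Day 14.

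**An inference to avoid.** From the printed 2B mark, a reader might infer that the two randomized arms have their platelets checked at different visits. The documents do not support this, because neighbouring 2B rows are visibly out of column.

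**Conclusion.** The point holds as a minor one, and the remedy is a cheap improvement. Followed as tabulated, Schedules 2A, 2C and 3 leave at least 250 of 400 Segment I doses, and all Segment II doses, without a scheduled platelet count before Day 21. A symptom-free fall in that time can meet a suspected-AESI criterion and go unrecorded. Section 6.1.5 does not settle whether this is intended. The 14-of-15 result rests only on the printed marks and the visit window.

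A reader might infer that the trial would miss TTS cases, or that second-dose safety is compromised. Neither follows. TTS is described as very rare, and a platelet fall alone is not TTS. Participants in 2C do not enter Segment II (Section 5.3). For those who do, a post-dose count (whichever day 2B intends) and the Day 56 count come before the second dose, and Section 7.5 withholds vaccination below 75,000. The primary endpoint is unaffected, and no between-arm test of platelet events is planned.

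**What to change.** State in Section 6.1.5 and in Schedules 2A, 2B, 2C and 3 that a platelet count is taken at both Day 14 and Day 28 after each dose (Days 70 and 84 in Segment II). Word the sentence so that the Day 28 restriction clearly applies to the mechanistic studies only. Check the 2B mark against the laid-out table while making the change.

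Blood is already drawn at these visits for the antibody tests, and the kits described at the start of Section 6 serve remote visits. The cost is a text and table correction and at most one extra CBC tube per dose: up to 400 in Segment I and up to 250 in Segment II. More counts will probably bring some additional suspected-AESI reports, because Section 1.5.2.1 notes that platelet counts fluctuate in this population.

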6.1.6 Day 90 (+/-15 Days) and 180 (+/- 30 Days)

This will be the last visit where the subject is directly contacted in Segment I, unless contact is made by the participant or the study team has follow-up queries. All updates to medications and therapies from last visit will be recorded. Patient and Graft Status of the patient as well as the COVID Surveillance and Evaluation will be recorded. Anti-SARS-CoV-2 spike protein antibody and anti-SARS-CoV-2 nucleocapsid total antibody will also be obtained during this visit. If necessary, a symptom directed physical exam can be performed.

6.1.7 Year 1 and 2 (+/- 60 Days)

Information for these visits will be obtained by review of the participant's medical record. This includes the participant's current medical status and any changes noted from last visit. Subjects will also have their immunosuppression medications recorded. Any SAEs, or AESIs will be documented and reported as necessary. The Patient and Graft Status CRFs will be completed. An anti-SARS-CoV-2 spike protein antibody and anti-SARS-CoV-2 nucleocapsid total antibody test will be performed at the Year 1 visit. These tests will only be performed at this time point if the antibody levels obtained at Day 180 are detectable. The Kidney Transplant Follow-Up, Safety Follow Up, and Risk Factor Assessment questionnaires will also be completed at the Year 1 follow up visit.

6.1.8 Mechanistic Studies

Specimen collections for mechanistic studies is detailed in section 3.1.4 Exploratory Mechanistic Immunologic Studies. This includes a table indicating the schedule of collections and testing to be performed. Samples will be collected as close to the timepoint as possible, but some variation is expected and will not be considered a deviation.

6.2 Segment II

This segment will be evaluating the dosing of the Janssen Ad26.COv2.S vaccine with immunosuppression adjustment of patients in Segment I who were maintained on their current immunosuppression and had a lack of response at Day 28. Lack of response for this study is defined as anti-SARS-CoV-2 spike protein levels <250 U/mL.

Study procedures for Segment II will proceed in the same manner and schedule as in Segment I with the absence of screening procedures and mechanistic studies excluding the anti-SARS-CoV-2 Nucleocapsid Total Antibody test. Samples collected for the anti-SARS-CoV-2 Nucleocapsid Total Antibody test will continue to be obtained and will align with the collection and timepoints noted for the anti-SARS-CoV-2 spike protein antibody test. As all subjects will experience a reduction in IS, the Nephrologist will confirm medication compliance with the adjusted IS regimen during the Nephrology consult prior to receiving the Janssen Ad26.CoV2.S on Day 56. See Schedule of Events 3: Segment II in Section 6.6 for more details on study procedures.

6.3 Initial Responders

Subjects who are randomized to this group will have had an anti-SARS-CoV-2 spike test result at screening ≥ 250 U/mL. As they are not categorized as having a low to non-response to their initial vaccine series, they will not be offered to receive the Janssen Ad26.CoV2.S vaccine. They will have follow up information collected to be used as a comparison to Segments I and II at Year 1 and Year 2. Blood samples will be collected for the Mechanistic Immunologic studies on Day 0, but otherwise all information collected will be by either patient contact or review of the medical record. This includes the subject's demographics, medical history, prior and concomitant medications and therapies, immunosuppression medications, COVID-19 surveillance and evaluation, patient and graft status. See Schedule of Events 1 under Section 6.6 for more details.

6.4 Unscheduled Visit

This visit will occur in Segments 1 and 2 if there are any medical event which would require follow up with a physician. This would be a clinical visit and contain a nephrology consult (if needed), a symptom directed physical exam, vital signs, and collection of the patient and graft status. This may include additional care if the sponsor-investigator believes it to be necessary for the health of the participant (COVID-19 surveillance, review of medications, etc.).

